5.3 Baseline

Baseline for the assessment of the ECG effect of CBP-307 (CBP-307 in Group 1 versus placebo in Groups 2A and 2B) will be time-matched values on Day -1 ([Table 3](#)).

For assay sensitivity in Groups 2A and 2B, the following baselines will be used:

- Group 2A: For moxifloxacin administered on Day 1 (defined as Period 1 Day 1), baseline will be Day 16 (defined as Period 1 Day -1), on which subjects are administered placebo. For placebo-correction in this group, placebo values will be derived from Day 15 (defined as Period 2 Day 1) on which subjects are administered placebo, and baseline will be obtained on Day -1 (defined as Period 2 Day -1).
- Group 2B: For moxifloxacin administered on Day 16 (defined as Period 2 Day 1), baseline will be Day 1 (defined as Period 2 Day -1), on which subjects are administered placebo. For the placebo-correction in this group, Day -1 (defined as Period 1 Day 1) values will be used as placebo (no treatment) and baseline will be obtained on Day 15 (defined as Period 1 Day -1).

For T-wave morphology and U-wave presence, baseline includes findings observed in any replicates from all time points that constitute baseline.

Table 3 Treatment administration and baseline definition

Day	Treatment Arm Group 1	Control Arm	
		Group 2A	Group 2B
-1	CBP-307 placebo Baseline for T1, T2, T3	CBP-307 placebo Baseline for T5 and T6; Baseline for T8 moxifloxacin- placebo on Day 15	CBP-307 placebo Baseline for T4, T5 and T6; T8: moxifloxacin-placebo on Day -1;
1	CBP-307 0.05 mg Moxifloxacin-placebo T1: CBP-307 0.05 mg on Day 1	400 mg Moxifloxacin CBP-placebo T7: moxifloxacin on Day 1	Moxifloxacin-placebo CBP-placebo T4: corresponding placebo on Day 1; Baseline for T7 on Day 16
6	CBP-307 0.2 mg T2: CBP-307 0.2 mg on Day 6	CBP-307-placebo T5: corresponding placebo on Day 6	CBP-307-placebo T5: corresponding placebo on Day 6
15	CBP-307 0.5 mg T3: CBP-307 0.5 mg on Day 15	CBP-307-placebo T6: corresponding placebo on Day 15 T8: moxifloxacin-placebo on Day 15	CBP-307-placebo T6: corresponding placebo on Day 15; Baseline for T8 moxifloxacin- placebo on Day -1
16	CBP-307 placebo Moxifloxacin-placebo (not analyzed)	CBP-307 placebo Moxifloxacin-placebo Baseline for T7 on Day 1	CBP-307 placebo 400 mg Moxifloxacin T7: moxifloxacin on Day 16

Note: To facilitate analysis, the nested crossover design for the moxifloxacin/placebo comparison for assay sensitivity needs to be coded following a 2-period crossover study design

with time-matched baseline on Day -1 in each period. The observations from Groups 2A and 2B will be relabeled (see [Table 4](#)). For example, for Group 2A, the moxifloxacin-placebo arm, baseline is Day 16 for the moxifloxacin day (Day 1) and baseline is Day -1 for the placebo day (Day 15). Therefore, Day 1 and Day 15 will be coded as Day 1, and Day -1 and Day 16 will be coded as Day -1.

Table 4 Period definition for Group 2A and 2B

		Period	Treatment Days (per Table 3)			
Sub-group	Treatment		-1	1	15	16
2A	Moxi/Placebo	Period 1 (Moxi)		Day 1		Day -1
		Period 2 (Placebo)	Day -1		Day 1	
2B	Placebo/Moxi	Period 1 (Placebo)	Day 1		Day -1	
		Period 2 (Moxi)		Day -1		Day 1

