6. STUDY TREATMENTS

The study treatment names and ordering to be used in the TFLs are presented in [Table 1](#).

Table 1: Presentation of Study Treatments in TFLs

Study Treatment	Order in TFLs
Placebo	1
400 mg Moxifloxacin	2
0.05 mg CBP-307	3
0.1 mg CBP-307	4
0.2 mg CBP-307	5
0.5 mg CBP-307	6

All TFLs will be based on actual treatments (eg, if subject was assigned to receive placebo but was wrongfully dosed with active treatment they would be summarized and listed under active treatment).

The study treatment sequence names, abbreviations, and ordering to be used in the TFLs are presented in [Table 2](#).

Table 2: Presentation of Study Treatment Sequences in TFLs

Study Treatment Sequence	Abbreviation	Order in TFLs
1 capsule of CBP-307 matched placebo on Day -1 -> 1 × 0.05 mg CBP-307 and 1 tablet of Moxifloxacin matched placebo on Day 1 -> 1 × 0.1 mg CBP-307 on Day 2 -> 2 × 0.1 mg CBP-307 on Days 3 to 6 -> 5 × 0.1 mg CBP-307 on Days 7 to 15 -> 1 capsule of CBP-307 matched placebo and 1 tablet of Moxifloxacin matched placebo on Day 16	Group 1	1
1 capsule of CBP-307 matched placebo on Day -1 -> 1 capsule of CBP-307 matched Placebo and 1 × 400 mg Moxifloxacin tablet on Day 1 -> 1 capsule of CBP-307 matched Placebo on Day 2 -> 2 capsules of CBP-307 matched Placebo Days 3 to 6 -> 5 capsules of CBP-307 matched Placebo on Days 7 to 15 -> 1 capsule of CBP-307 matched placebo and 1 tablet of Moxifloxacin matched placebo on Day 16	Group 2A	2
1 capsule of CBP-307 matched placebo on Day -1 -> 1 capsule of CBP-307 matched Placebo and 1 tablet of Moxifloxacin matched placebo on Day 1 -> 1 capsule of CBP-307 matched Placebo on Day 2 -> 2 capsules of CBP-307 matched Placebo Days 3 to 6 -> 5 capsules of CBP-307 matched Placebo on Days 7 to 15 -> 1 capsule of CBP-307 matched placebo and 1 × 400 mg Moxifloxacin tablet on Day 16	Group 2B	3

The summaries will be based on planned treatment sequences and listings will be based on actual treatment and sequences.

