6.4 Categorical Analysis

Results for categorical outliers will be summarized in frequency tables with counts and percentages for both number of subjects and number of time points. Subject data will be summarized using the count of distinct subjects that fall into the category and the percentage of the total number of subjects. Time point data will be summarized using the count of time points at which the assessments fall into the category and the percentage of the total number of time

points at which assessments are performed. Counts (either number of subjects or number of time points) for each treatment group will be used as the denominator in the calculation of percentages unless otherwise specified.

A subject or time point will be determined as an outlier if the following criteria (which are assessed separately) are met for the ECG intervals ([Table 5](#)).

Table 5 Criteria for determining a subject or time point outlier

ECG interval	Categorical outlier criteria
QTcF	Treatment-emergent value of > 450 and ≤ 480 ms when not present at baseline (new onset)
	Treatment-emergent value of > 480 and ≤ 500 ms when not present at baseline (new onset)
	Treatment-emergent value of > 500 ms when not present at baseline (new onset)
	Increase of QTc from baseline of > 30 and ≤ 60 ms
	Increase of QTc from baseline > 60 ms
PR	Increase of PR from baseline $> 25\%$ resulting in PR > 200 ms
QRS	Increase of QRS from baseline $> 25\%$ resulting in QRS > 120 ms
HR	Decrease of HR from baseline $> 25\%$ resulting in HR < 50 bpm
	Increase of HR from baseline $> 25\%$ resulting in HR > 100 bpm

All outliers will be summarized for each treatment on the basis of incidence rates. A subject will be counted only once for a particular outlier event if the subject experiences more than 1 episode of that event. The total number of time points will be based on the number of observed time points across all subjects within a treatment group.

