6.5 Morphological analysis for T-wave and U-wave

Morphological analyses will be performed with a focus on detecting changes in T-wave morphology and appearance of abnormal U-waves. The analyses will evaluate change-from-baseline (i.e., treatment-emergent changes). For each category of T-wave morphology and of U waves, the category will be deemed as present if observed in any replicates at the time point. For baseline, the category will be deemed as present if observed in any replicates from all time points that constitute baseline.

The analysis results for T-wave morphology and U-wave presence will be summarized in frequency tables with counts and percentages for both number of subjects and number of time points. The number and percentage of subjects in each treatment group having changes from baseline that represent the appearance of the morphological abnormality will be also summarized. The total number of time points having a particular change event will be summarized in terms of number and percentage based on the number of observed time points across all subjects within a treatment group.

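### In two of the four moxifloxacin-analysis cells the baseline day falls 15 days after the treatment day, so new-onset and treatment-emergent counts are wrongly defined there

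*SAP*

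**What the plan says.** The SAP file holds a main SAP and a separate cardiodynamic SAP from the central ECG laboratory. Section 5.3 of the cardiodynamic SAP, with its Tables 3 and 4, sets the day pairs for the moxifloxacin comparison in Group 2:

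- 2A moxifloxacin (T7): "For moxifloxacin administered on Day 1 (defined as Period 1 Day 1), baseline will be Day 16".
- 2A placebo (T8): "placebo values will be derived from Day 15 (defined as Period 2 Day 1) on which subjects are administered placebo"; its baseline is Day -1.
- 2B moxifloxacin (T7), given on Day 16: "baseline will be Day 1 (defined as Period 2 Day -1), on which subjects are administered placebo".
- 2B placebo (T8): "Day -1 (defined as Period 1 Day 1) values will be used as placebo (no treatment) and baseline will be obtained on Day 15".

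The note to Table 3 explains this as recoding a nested crossover into two periods.

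Table 5 in Section 6.4 defines an absolute QTcF outlier in the form "Treatment-emergent value of > 500 ms when not present at baseline (new onset"). Its other criteria are changes from baseline. Section 6.5 treats change from baseline as treatment-emergent and adds: "For baseline, the category will be deemed as present if observed in any replicates from all time points that constitute baseline". Table 2 in Section 5.2 restricts the categorical set to post-baseline time points with a usable baseline. No separate baseline rule is given for the moxifloxacin Tables 14.1.7.2, 14.1.8.2, 14.1.9.2 and 14.1.10.2.

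Table 2 in Section 6 of the main SAP gives the dosing. For 2B it lists "1 capsule of CBP-307 matched Placebo and 1 tablet of Moxifloxacin matched placebo on Day 1"; for 2A the placebo tablet comes on Day 16. On Days -1 and 15 both sub-groups receive CBP-307 placebo capsules only.

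**The concern.** A treatment-emergent finding is one that was absent before treatment and appears after it. If the baseline is recorded after the treatment, the comparison cannot show this. Categorical outliers and treatment-emergent T-wave and U-wave changes are stated secondary endpoints (Section 4.3), and their moxifloxacin tables are the positive-control reference for the same CBP-307 tables.

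Three errors can follow in 2A. A finding already present on Day -1 and Day 1 but absent on Day 16 is credited to moxifloxacin. A real Day 1 finding that persists to Day 16, or recurs then, is removed. A subject who receives moxifloxacin on Day 1 and leaves before Day 16, for whatever reason, has no baseline and disappears from the counts. In 2B, a finding on Day -1 that is gone by Day 15 is counted as emergent on placebo, although no moxifloxacin-placebo tablet had been given.

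The label is a separate fault. Table 3 calls Day 15 (2A) and Day -1 (2B) moxifloxacin-placebo, while the treatment entries in the same cells and the dosing table show CBP-307 placebo alone.

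**Working it through.** **Inputs.** Day pairs come from cardiodynamic SAP Section 5.3 and Tables 3 and 4. Tablet days come from main SAP Table 2. The sub-group size of 17 is from cardiodynamic SAP Section 6.6. Main SAP Section 5 has 16 per sub-group, which leaves the fractions unchanged. Day -1 is the day before Day 1.

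**Step 1: order of baseline and treatment.**

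| Cell | Treatment day | Baseline day | Baseline later? | Placebo tablet on T8 day? |
|---|---|---|---|---|
| 2A T7 | 1 | 16 | yes, by 15 days | not applicable |
| 2A T8 | 15 | -1 | no | no |
| 2B T7 | 16 | 1 | no | not applicable |
| 2B T8 | -1 | 15 | yes, by 15 days | no |

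Two of four cells are reversed: 17 of 34 T7 subject-days and 17 of 34 T8 subject-days. T1 to T6, the CBP-307 analysis, all use Day -1, so none of those is reversed.

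**Step 2: effect on counts (illustrative rates, not from the documents).** Let a finding be present on a share e of early days and l of late days, independently. A forward cell counts l(1 - e); a reversed cell counts e(1 - l).

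- e = l = 10%: both give 0.10 × 0.90 = 9.0%.
- e = 5%, l = 15%: forward 0.15 × 0.95 = 14.25%, reversed 0.05 × 0.85 = 4.25%, average 9.25%. T7 and T8 share this average, because each has one forward and one reversed cell.
- If a share r of findings that emerge on Day 1 in 2A persists to Day 16, the share of moxifloxacin-emergent findings counted over both sub-groups is 1 - r/2: 87.5% at r = 0.25, 75% at r = 0.5 and 50% at r = 1.
- If 10% of subjects have a finding at entry and half lose it by Day 15 or 16, each reversed cell gains 17 × 0.10 × 0.5 = 0.85 falsely emergent subjects.

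**Step 3: the plan's own assay-sensitivity figures (Section 6.6).** Effect size: 5/(1.24 × √24) = 0.823 (stated 0.82). One-sided 5% paired t-test, n = 28, effect size 0.64: power 95.1% (stated at least 95%). SD limit: 5.4 × 0.82/0.64 = 6.92 ms (stated 6.9). All reproduce.

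**Step 4: the continuous contrast.** Write D for the QTcF value on a day.

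- 2A as planned: (D1 - D16) - (D15 - D-1) = D1 + D-1 - D15 - D16.
- 2A with adjacent days: (D1 - D-1) - (D16 - D15) = D1 - D-1 + D15 - D16.

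The moxifloxacin day minus the placebo-tablet day, D1 - D16, has the same sign and weight in both. If a subject's level is E in the first week and L in the third, the planned contrast contains 2(E - L) and the adjacent one contains 0. In 2B the sign is reversed, so the mean shift cancels when 2A and 2B are equal in size. With nA and nB completers and a mean drift d = L - E, the remaining bias is 2d(nB - nA)/(nA + nB). For an assumed 16:12 split and d of 1 to 3 ms it is -0.29 to -0.86 ms. The assay-sensitivity model in Section 6.2 has no period or sequence term to absorb it.

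**The case against.** The pairing is deliberate and disclosed, assay sensitivity is decided by the slope and the lower confidence bound rather than by these counts, and T7 and T8 carry the same mix of directions. All of this stands, and it limits the point. It does not give a post-treatment day the meaning of a baseline in a new-onset count.

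A reader might infer three stronger claims that the documents do not support.

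- *All emergent counts are invalid.* The CBP-307 tables are untouched, and the forward half of the moxifloxacin cells is correctly ordered. With stable prevalence and no persistence, the two directions even give the same expected rate.
- *Missing placebo tablets bias the moxifloxacin effect.* They do not when 2A and 2B are balanced: the tablet effect is removed when the placebo-tablet day is subtracted as the T7 baseline (Step 4).
- *Assay-sensitivity power falls below 95%.* Adding an assumed between-subject SD s of the early-to-late shift gives a total SD of √(6.07² + 4s²), where 6.07 = 1.24 × √24. For s = 2, 3 and 4 ms this is 7.27, 8.54 and 10.05 ms, with power of 97.1%, 91.5% and 82.2% at n = 28, against 99.5% at s = 0. But s is not in the documents, and the 1.24 ms comes from a similarly designed study that may already contain this shift. The models also adjust for baseline: with effective weight k on baseline, the shift enters as 1 + k as planned and 1 - k with adjacent days, so 2 against 0 holds only at k = 1. Finally, Section 6.6 promises 95% only within a variability limit, which on this scale is 5/0.64, or about 7.8 ms. The two larger cases breach that condition; they do not contradict the figure.

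**Conclusion.** The point holds for the moxifloxacin categorical and morphology tables. In two of four cells, half of the planned subject-days in each column, the baseline is 15 days later than the treatment, and the plan as written will report new-onset and treatment-emergent counts that do not mean what they say. This follows from the documents alone. How many subjects would be misclassified depends on prevalence and persistence, which the documents do not give. The comparison of T7 with T8 is roughly balanced in direction, but the absolute incidences cannot be read as emergent rates, and persistent moxifloxacin findings in 2A are masked. The moxifloxacin-placebo label on the T8 days contradicts the dosing table.

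For the continuous assay-sensitivity analysis, the planned pairing is unbiased with equal 2A and 2B completers but does not cancel a subject's early-to-late shift. The size of any power loss is not established and should not be claimed.

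**What to change.** In Section 5.3 and Tables 3 and 4, add a day assignment for the moxifloxacin categorical and morphology analyses (Sections 6.4 and 6.5; Tables 14.1.7.2, 14.1.8.2, 14.1.9.2 and 14.1.10.2) that uses the tablet days, each with the preceding day as baseline:

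- 2A: T7 = Day 1, baseline Day -1; T8 = Day 16, baseline Day 15.
- 2B: T8 = Day 1, baseline Day -1; T7 = Day 16, baseline Day 15.

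Period 1 is then Days -1 and 1, and Period 2 is Days 15 and 16. Every baseline precedes its treatment day, T8 is the day on which the placebo tablet was given, and a Group 2 subject who leaves before Day 15 keeps a complete first period.

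Correct the T8 label in Table 3: wherever Day 15 (2A) and Day -1 (2B) stay in use as control days, call them CBP-307 placebo only.

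Optionally, run the Section 6.2 model with the same pairing as a sensitivity analysis.

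Cost: SAP wording and recoding of two tables. All four Holter days are already recorded; dosing, visits and data collection do not change.

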5.4 QT Correction Methods

The QT and RR value for each beat will be used for HR correction.

The Fridericia's correction (QTcF) is defined as $QTcF \text{ (ms)} = QT \text{ (ms)} / [RR(\text{ms})/1000]^{1/3}$.

For evaluation of the HR-corrected QT interval, a scatter plot and decile plot of QTc and RR intervals by treatment with a regression line and a linear mixed-effects line (90% CI), respectively, will also be given.

5.5 Terminology and Definitions: Placebo-corrected $\Delta QTcF$ and Placebo-adjusted $\Delta\Delta QTcF$ ($\Delta\Delta QTcF$)

Change-from-baseline QTcF ($\Delta QTcF$) will be used as the dependent variable in the concentration-QTc analysis and in the by-time point analysis.

By-time point analysis

Placebo-corrected $\Delta QTcF$ ($\Delta\Delta QTcF$)

- In the by-time point analysis on the QTcF interval, LS mean, SE, and 2-sided 90% CI of $\Delta QTcF$ will be calculated for CBP-307 on Day 1, 6, and 15, for moxifloxacin and for placebo for CBP-307, and placebo for moxifloxacin at each post-dose time point. LS mean, SE, and 2-sided 90% CI of $\Delta\Delta QTcF$ will be calculated for each CBP-307 dose group and for moxifloxacin group at each post-dose time point.

Concentration-QTc analysis

Placebo-corrected $\Delta QTcF$ ($\Delta\Delta QTcF$)

- In the concentration-QTc analysis, the term placebo-corrected $\Delta QTcF$ ($\Delta\Delta QTcF$) will be used for the model-predicted effect across concentrations on a population level.

- *Definition:* Model-predicted mean $\Delta QTcF$ in each CBP-307 dose group (or moxifloxacin group) minus model-predicted mean $\Delta QTcF$ in the respective placebo group, which equals slope estimate \times concentration + treatment effect-specific intercept.
 - The term placebo-corrected $\Delta QTcF$ ($\Delta\Delta QTcF$) will be used for the model-predicted effect on the $QTcF$ interval in the concentration- QTc prediction table and the scatter plots for concentration- QTc model(s), decile plots, and prediction plots, as described in [Section 8](#).

Placebo-adjusted $\Delta QTcF$ ($\Delta\Delta QTcF$)

- In the concentration- QTc analysis, the term placebo-adjusted $\Delta QTcF$ ($\Delta\Delta QTcF$) will be used to illustrate the underlying data on both subject and population levels.
- *Definition for the estimated placebo-adjusted $\Delta QTcF$ on a subject level:* observed $\Delta QTcF$ for each subject (on each CBP-307 dose group or moxifloxacin group or placebo group) minus the estimated time effect (i.e., the model-predicted mean $\Delta QTcF$ in the placebo group).
 - This term will be used to illustrate the underlying data on a subject level in the scatter plot(s) for concentration- QTc model(s), as described in [Section 8](#).
- *Definition for the estimated placebo-adjusted $\Delta QTcF$ term on a population level:* the average of individually estimated placebo-adjusted $\Delta QTcF$ values at the associated median plasma concentration within each concentration decile.
 - This term will be used to illustrate the underlying data on a population level in the decile plot(s), as described in [Section 8](#).

6 Analysis

6.1 Concentration- QTc Analysis (Primary Analysis)

The relationship between CBP-307 plasma concentrations and change-from-baseline $QTcF$ ($\Delta QTcF$) will be quantified using a linear mixed-effects modeling approach with $\Delta QTcF$ as the dependent variable, time-matched concentrations of CBP-307 as the exploratory variate (0 for placebo), treatment (active=1 or placebo=0), and time (i.e., post-baseline time points on Days 1, 6, and 15: categorical) as fixed effects, and a random intercept and slope for concentrations per subject (Garnett et al¹). Centered baseline $QTcF$ (i.e., baseline $QTcF$ for individual subject minus the population mean baseline $QTcF$ for all subjects) will be included in this model as an additional covariate. If necessary, a sensitivity analysis will be performed using the model without this term. CBP-307 plasma concentrations below the quantifiable limit at pre-dose will be set to zero and after dosing will be set to 1/2 the lower limit of quantitation in the concentration- QTc analysis.

An unstructured covariance matrix will be specified for the random effects. If convergence cannot be achieved even after appropriate rescaling of the concentrations, the random effect on the slope and intercept will be dropped, in this order, until convergence is achieved. The degrees of freedom of estimates will be determined by the Kenward-Roger method. From the model, the slope (i.e., the regression parameter for concentration) and the treatment effect-specific intercept

(defined as the difference between CBP-307 and placebo) will be estimated together with the 2-sided 90% CI. The estimates for the time effect will be reported with degrees of freedom and SE.

For the assessment of the ECG effect of CBP-307 versus placebo, the time term incorporated into the models (both by-time point analysis and concentration-QTc analysis [or assay sensitivity]) includes the single pre-dose time point and all post-dose time points on Days 1, 6, and 15, and Days 1 and 16 for active versus placebo and moxifloxacin versus placebo, respectively. All times are relative to the time of dosing on that day which is considered the first dose for the assay sensitivity analysis. For the analysis of CBP-307 versus placebo, the first dose of study treatment is on Day 1.

The geometric mean of the individual C_{max} values for subjects in CBP-307 group on each day of Days 1, 6, and 15 will be determined, respectively. The population point estimate and its 2-sided 90% CI for the $\Delta\Delta QTcF$ (i.e., slope estimate \times concentration + treatment effect-specific intercept) interval at these geometric mean C_{max} will be obtained. If the upper bound of the 2-sided 90% CI of the predicted $\Delta\Delta QTcF$ effect at the observed geometric mean C_{max} of CBP-307 on Days 6 and 15 is below 10 ms, it will be concluded that CBP-307 does not cause clinically relevant QTc prolongation within the observed plasma concentration ranges.

To evaluate the adequacy of model fit with respect to the assumption of linearity, the observed $\Delta QTcF$ values adjusted by population time effect estimated from the model will be used. These individual placebo-adjusted $\Delta QTcF_{i,k}$ ($\Delta\Delta QTcF_{i,k}$) values are derived as the observed individual $\Delta QTcF_{i,k}$ for subject i administered with CBP-307 or placebo at time point k minus the estimated population mean placebo effect at time point k (i.e., time effect). A decile plot of observed drug concentrations and the mean placebo-adjusted $\Delta QTcF$ ($\Delta\Delta QTcF$) and 90% CI at the median concentration within each decile will be given. The regression line presenting the model-predicted $\Delta\Delta QTcF$ (as described by Tornøe et al²) will be added to evaluate the fit of a linear model and visualize the concentration-response relationship. Additional exploratory analyses (via graphical displays and/or model fitting) will include assessing for a delayed effect (hysteresis, [Section 6.1.1](#)) and the justification for the choice of the pharmacodynamic model (linear versus nonlinear, [Section 6.1.2](#)) as follows.

The SAS code for the concentration-QTc analysis is as follows.

```
PROC MIXED DATA=PKPD method=reml;
CLASS SUBJID TIME;
MODEL DQTc=TRT CONC TIME CBASE / solution cl noint alpha=0.1 alphap=0.1 COVB DDFM=KR;
RANDOM INT CONC /TYPE=UN SUBJECT=SUBJID s;
ESTIMATE 'Pred Mean Diff for T1' TRT 1 CONC &GeoMeanCmax_1 / CL ALPHA=0.1;
RUN;
```

Where PKPD = PK/QTc population, SUBJID = subject ID, TRT = treatment (1 for CBP-307, and 0 for placebo = 0), TIME = nominal post-baseline time point, CONC = plasma concentration of CBP-307, CBASE = centered baseline QTcF, T1 = active dose on Day 1, GeoMeanCmax_1 = geometric mean C_{max} for T1, DQTc = $\Delta QTcF$.

Note: ESTIMATE statements will be repeated for active dose groups on Days 6, and 15.

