4.1 ECG and Pharmacokinetic Sample Collection

Continuous Holter ECG recordings will be performed before dosing for 25 hours on Days -1, 1, 6, 15, and 16 and continue through 12 or 24 hours post-dose. Replicate 12-lead ECGs will be extracted from the continuous recording prior to dosing (-30 minutes) and 0.5, 1, 2, 3, 4, 6, 8, 12, and 24 hours post-dose on each day. At each time point, up to 10 ECG replicates will be extracted from a 5-minute time window (the last 5 minutes of the 15-minute period when the subject is maintained in a supine, quiet position). The ECG effects of CBP-307 will be tested on data from Day -1 (baseline for both groups), Day 6 (therapeutic concentrations versus placebo), and Day 15 (supratherapeutic concentrations versus placebo). Assay sensitivity with moxifloxacin will be evaluated using ECG data collected on Days -1, 1, 15, and 16.

Pharmacokinetic blood samples will be collected at the following time points: prior to dosing and 0.5, 1, 2, 3, 4, 6, 8, 12, and 24 hours after dosing on each PK sampling day (Days 1, 6, 15, and 16; sample collection windows are as follows: ± 2 minutes for 0.5 hours post-dose, ± 5 minutes for 1 to 4 hours post-dose, ± 10 minutes for 6 to 8 hours post-dose, and ± 30 minutes for 12 to 24 hours post-dose). Additional PK samples will be collected at 72 and 96 hours following dosing on Day 15 (sample collection window: ± 30 minutes).

All Holter/ECG data will be collected using M12R continuous 12-lead digital recorders and the M12A Enterprise Holter System Client (Global Instrumentation, LLC, Manlius, NY, USA). The equipment will be supplied and supported by ERT.

ECG intervals will be measured by the core laboratory in a blinded manner using the Early Precision QT technique (EPQT) (see [Appendix A](#) for more details). The ECG database will be locked before any statistical analysis is undertaken.

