6.2 Assay Sensitivity

The analysis to show assay sensitivity will be based on the concentration-QTc analysis of the effect on $\Delta\Delta\text{QTcF}$ of 400 mg oral moxifloxacin using a similar model as for the primary analysis. That is, the relationship between moxifloxacin plasma concentration and ΔQTcF will be investigated by linear mixed-effects modeling. The model will include ΔQTcF as the dependent variable, moxifloxacin plasma concentration as the explanatory variable (0 for placebo), study treatment (1 for moxifloxacin and 0 for placebo) and time (i.e., post-baseline time point on Day 1

as defined in Table 4 for each period) as fixed effects, and random effects on intercept and slope per subject (Garnett et al¹). Centered baseline QTcF will be included in this model as an additional covariate. If necessary, a sensitivity analysis will be performed using the model without this term. The geometric mean of the individual C_{max} values for subjects receiving the single dose of 400 mg moxifloxacin will be determined. The predicted effect and its 2-sided 90% CI for $\Delta\Delta QTcF$ (i.e., slope estimate \times concentration + treatment effect-specific intercept) at this geometric mean C_{max} will be obtained.

If the slope of the moxifloxacin plasma concentration/ $\Delta QTcF$ relationship is statistically significant at the 10% level in a 2-sided test and the lower bound of the 2-sided 90% CI of the predicted QT effect at the observed geometric C_{max} of the 400 mg dose is above 5 ms, assay sensitivity will be deemed to have been demonstrated.

The SAS code for the concentration-QTc analysis is as follows.

```
PROC MIXED DATA=PKPD method=reml;
CLASS SUBJID TIME;
MODEL DQTc=TRT CONC TIME CBASE / solution cl noint alpha=0.1 alphap=0.1 COVB DDFM=KR;
RANDOM INT CONC /TYPE=UN SUBJECT=SUBJID s;
ESTIMATE 'Pred Mean Diff for T7' TRT 1 CONC &GeoMeanCmax_1 / CL ALPHA=0.1;
RUN;
```

Where PKPD = PK/QTc population, SUBJID = subject number, TRT = treatment (1 for moxifloxacin = 1 and 0 for placebo), TIME = nominal post-baseline time point on Day 1, CONC = plasma concentration of moxifloxacin, CBASE = centered baseline QTcF, T7 = moxifloxacin group, GeoMeanCmax_1 = geometric mean C_{max} for T7, DQTc = $\Delta QTcF$.

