6.6 Determination of Sample Size

Approximately 68 healthy subjects (at least 30% for each sex) will be randomized into 2 groups (Group 1 and 2) with 34 subjects in each. Group 2 consists of 2 sub-groups (Group 2A and 2B) and each sub-group will be randomized with 17 subjects.

Determination of sample size for primary analysis

A sample size of 28 evaluable subjects per treatment group will provide more than 94.4% power to exclude that CBP-307 causes more than 10-ms QTc effect at clinically relevant plasma levels, as shown by the upper bound of the 2-sided 90% confidence interval (CI) of the model-predicted QT effect ($\Delta\Delta\text{QTcF}$) at the observed geometric mean C_{max} of CBP-307 in the study. This power is estimated approximately using a 2-sample t-test. The calculation assumes a 1-sided 5% significance level, an underlying effect of CBP-307 of 3 ms and a standard deviation (SD) of the ΔQTcF of 8 ms for both CBP-307 and placebo treatment groups. Note that this calculation is conservative, since it does not take into account any gain in precision due to the use of all data of each subject with the help of a linear mixed-effects model. The concentration-QTc analysis method is supported by Darpo et al⁵ and Ferber et al⁶, and consistent with the experiences from 25 recent TQT studies.

Determination of sample size for assay sensitivity analysis

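### The primary model's convergence fallback can end with no within-subject correlation, which would make the 10 ms upper bound too low in the unlikely case that the last step is reached

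*SAP*

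**What the plan says.** All references are to the cardiodynamic SAP.

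- **Planned model (Section 6.1).** A linear mixed model for the change from baseline in QTcF, with a random intercept and a random concentration slope per subject: "An unstructured covariance matrix will be specified for the random effects". Degrees of freedom are by Kenward-Roger.
- **Code (Section 6.1).** The within-subject structure is the single line "RANDOM INT CONC /TYPE=UN SUBJECT=SUBJID s". There is no REPEATED statement.
- **Fallback (Section 6.1).** After rescaling of the concentrations, "the random effect on the slope and intercept will be dropped, in this order, until convergence is achieved". No replacement covariance and no robust variance is named.
- **Records per subject.** The time term "includes the single pre-dose time point and all post-dose time points on Days 1, 6, and 15". Section 4.1 sets the ECG extractions at one pre-dose point and "0.5, 1, 2, 3, 4, 6, 8, 12, and 24 hours post-dose on each day".
- **Decision (Section 6.1).** If the upper limit of the two-sided 90% interval at the geometric mean Cmax "on Days 6 and 15 is below 10 ms, it will be concluded that CBP-307 does not cause clinically relevant QTc prolongation".
- **Contrast (Section 6.3).** When the by-time point model for CBP-307 fails to converge, it is fitted by day and moves to compound symmetry and then autoregressive structures. Correlation within subject is retained throughout.

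**The concern.** The sequence is: unstructured intercept and slope, then intercept only, then neither. At the last stage every record has an independent error. Kenward-Roger cannot repair this, because no covariance structure is left for it to adjust.

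The records are not plausibly independent. They come from the same person, and on all three days each clock time is compared with the same time-matched Day -1 value (Section 5.3), which by itself induces positive correlation. Because CBP-307 and placebo are compared between subjects, ignoring that correlation makes the standard error too small and the upper limit too low. That limit is the quantity on which the 10 ms conclusion rests.

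**Working it through.** **1. The plan's own figure.** Section 6.6 states "A sample size of 28 evaluable subjects per treatment group will provide more than 94.4% power", from a two-sample t-test with a 3 ms effect, a 10 ms margin, SD 8 ms and one-sided 5%. Standard error of the difference: 8 × √(2/28) = 2.138 ms. Noncentrality: (10 − 3)/2.138 = 3.27 on 54 degrees of freedom. Power: 94.38%. The stated figure reproduces.

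**2. Records per subject.** 1 pre-dose + 9 post-dose = 10 per day. Over three days that is 30 in Groups 1 and 2B (28 if only one pre-dose point in all is kept). Group 2A takes moxifloxacin on Day 1 and contributes 20. With 28 per arm: 28 × 30 + 14 × 30 + 14 × 20 = 1,540 records.

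**3. Simple closed form** (28 v 28, m = 30 records each, SD 8 ms):

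- Independence SE = 2.138/√30 = 0.39 ms.
- Correct SE = 2.138 × √[(1 + 29 × ICC)/30] = 0.77 (ICC 0.1), 1.22 (0.3), 1.54 (0.5), 1.80 ms (0.7).

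The SE is understated 2.0- to 4.6-fold. At ICC 0 nothing is lost.

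**4. The SAP's fixed-effects design** (treatment, concentration, 30 time points, centred baseline; Group 2A without Day 1), by exact covariance algebra. Assumptions not in the SAP: the ICC, a 25 h half-life, dose-proportional concentrations with 30% CV, and correlation at subject level only.

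- Reported SE: what ordinary least squares prints.
- True SE: the actual sampling SD of that estimate.
- Shift in limit = 1.645 × (random-intercept SE − reported SE), from unrounded values.
- Pass rate at a true 10 ms effect on that day = Φ(−1.645 × reported SE / true SE).

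| Day | ICC | Reported SE | True SE | Random-intercept SE | Shift in limit (ms) | Pass rate at 10 ms |
|---|---|---|---|---|---|---|
| 6 | 0.1 | 0.43 | 0.81 | 0.80 | 0.61 | 19% |
| 6 | 0.3 | 0.42 | 1.26 | 1.24 | 1.34 | 29% |
| 6 | 0.5 | 0.42 | 1.59 | 1.56 | 1.87 | 33% |
| 6 | 0.7 | 0.42 | 1.88 | 1.83 | 2.31 | 36% |
| 15 | 0.1 | 0.66 | 1.00 | 0.95 | 0.48 | 14% |
| 15 | 0.3 | 0.64 | 1.45 | 1.31 | 1.11 | 24% |
| 15 | 0.5 | 0.66 | 1.79 | 1.61 | 1.55 | 27% |
| 15 | 0.7 | 0.63 | 2.09 | 1.85 | 2.01 | 31% |

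At ICC 0 the pass rate is 5% on both days. The rates are for each day singly; the SAP's rule needs both days to pass.

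**5. At the planned 3 ms effect** (Day 15, ICC 0.5): the limit would read 3 + 1.645 × 0.66 = about 4.1 ms, against 3 + 1.645 × 1.61 = about 5.6 ms. Both are well below 10 ms.

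**6. How likely the step is.** An intercept-only model seldom fails unless its variance is near zero. In simulated trials of this layout, the intercept variance was estimated as zero in under 4% at ICC 0.02 and in none at ICC 0.05, 0.1, 0.3 or 0.5. A zero estimate is not itself non-convergence.

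**The case against.** The best defence is that the step is almost self-protecting. It is reached only after the full model fails, rescaling fails and the intercept-only model fails. When correlation is large enough to matter, the intercept-only model fits easily; when its variance is near zero, dropping it costs little. This largely stands. The pass rates in the table are conditional on ordinary least squares being the model used. They are not error rates of the sequential rule, which were not computed and would be much closer to nominal.

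The defence is not complete. A near-zero subject variance does not guarantee independence: with no subject-level variance but 30% of the variance at subject-by-day level (assumed), ordinary least squares still passes at 19-20% when the true effect is 10 ms. An intercept would normally pick up part of that correlation, so the step would again be unlikely, but the rule as written still permits an invalid interval.

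It could also be said that going straight from intercept and slope to intercept only is crude. It is a legitimate reduction that keeps within-subject correlation. An intermediate step with uncorrelated effects is a preference, not a correction.

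A reader might infer that the same fallback would wrongly favour assay sensitivity, since Section 6.2 describes the moxifloxacin analysis as "using a similar model as for the primary analysis". The SAP does not support that. Section 6.2 states no fallback rule, and each Group 2 subject supplies both moxifloxacin and placebo data (Section 5.3, Table 4). In that within-subject contrast, subject-level correlation leaves the least-squares SE about right: 0.80 ms reported against 0.80 ms true in a simulation with an assumed 30% subject-level share. Clustering within subject and period would make it too small, but a retained subject intercept would not cure that.

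**Conclusion.** The point holds for Section 6.1 as a contingency error. The SAP permits, as its last convergence step, a primary interval that ignores all within-subject correlation, while Section 6.3 retains a covariance structure in the same situation. If the step is reached with correlation present, the upper limit is about 0.5 to 2.3 ms too low and the per-day chance of wrongly excluding a true 10 ms effect is roughly 14-36% instead of 5%. These sizes rest on an assumed ICC of 0.1 to 0.7 and on the assumed concentration profile.

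A reader might take those rates as the trial's actual error risk, or the limit as far too low in general. Neither follows. The step is unlikely to be reached, and a shift of this size matters only when the true effect is near 10 ms. The point is worth correcting but is not a must-fix.

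**What to change.** In Section 6.1, end the dropping sequence at the random intercept. Add that if the intercept-only model fails, or its variance is estimated as zero, the model will be fitted with a within-subject REPEATED covariance (compound symmetry or autoregressive, as Section 6.3 already does) or with subject-clustered (EMPIRICAL) standard errors, and never with independent errors. A step with uncorrelated intercept and slope (TYPE=VC) before the slope is dropped is optional. No change to Section 6.2 is needed on this account.

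The cost is SAP wording, with no effect on the planned analysis if the model converges. In the rare fallback case the interval is slightly wider than least squares would give, as it should be.
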